4.5.2 Variables of Interest (or Endpoint) Required to Address the Scientific Question

The co-primary endpoints to be obtained for each subject in this study to address the scientific question are tissue eosinophil responders (as defined in Section [4.1](#)) at Week 24 and change in TSS from baseline to Weeks 23–24 as measured by the PRO questionnaire.

4.5.3 Treatment

AK002 or placebo administered to subjects on Days 1, 29, 57, 85, 113, and 141.

4.5.4 Intercurrent Events

The events below are considered ICE confounding with the efficacy outcomes.

- Premature discontinuation from the study.
- Use of prohibited/restricted medication.

Further clarification and handling of ICE including prohibited/restricted medications will be detailed in the statistical analysis plan (SAP).

4.5.5 Strategy for Handling Intercurrent Events

For the analysis of the trial product estimand, tissue eosinophil values and TSS will be counted as non-responders for binary variables and set to missing for continuous outcomes from the point when an ICE occurs. An appropriate method for handling missing data through statistical modeling, e.g., multiple imputation (MI) will be used. The estimand will provide an answer to the question that is crucial to individual subjects, “If I take this study medication as part of my treatment regimen, without adding any further medications that may impact the underlying disease or exit the study prematurely, what improvements in histology and PRO symptoms might be anticipated after 24 weeks?”

5. Study Design

5.1 Study Overview

This is a Phase 3, multicenter, randomized, double-blind, placebo-controlled study to evaluate the efficacy and safety of AK002 in patients with moderately to severely active EoD without EG who have an inadequate response with, lost response to, or were intolerant to standard therapies.

Patients enrolled in the study will receive 6 infusions of placebo or AK002 administered every 4 weeks and will be followed for 12 weeks after last dose unless patients elect to enter the optional open-label extension (OLE) period of the study.

Patients will be consented and then screened for 21–45 days prior to Day 1. Patients who meet all eligibility criteria can be enrolled into the study. Patients who do not meet all eligibility criteria at screening, or who qualify at screening but are not enrolled, may be assigned a new patient identification number and rescreened once. Patients rescreened within 30 days of signing the initial consent will not need to sign a new informed consent form (ICF) if no changes have been made to the ICF.

Patients will undergo EGD and colonoscopy with biopsy at screening and again 4 weeks after last dose. The EGD and colonoscopy should take place on the same day in order to minimize effects of procedure premedication on the PRO scores. For patients with a history of EoE and/or with a score of ≥ 3 on the dysphagia question on at least 1 day during screening, esophageal

biopsies will also be collected at screening and postdose. Biopsies from the gastric mucosa, duodenum, colon, and esophagus (as applicable) will be taken and reviewed by a central pathology reader. Additional biopsies will be collected for exploratory analysis.

The study is designed as follows:

- A screening period of 21–45 days with baseline evaluations for study eligibility, including active symptoms of disease (gathered by the patient reported outcome [PRO] questionnaire completed during screening) and EGD and colonoscopy (performed on the same day) with biopsy.
- Stool antigen test for *Helicobacter pylori* (*H. pylori*) will be assessed during screening to confirm no active *H. pylori* infection exists. If *H. pylori* is detected in tissue biopsies by the central pathologist, the patient should be excluded from the study.
- Prior EGD and colonoscopy biopsy samples may be used for eligibility as long as they were performed within 45 days of the screening window for the AK002-021 study and were performed and centrally assessed using the same criteria as for the AK002-021 study.
- If patients meet histology and symptom eligibility criteria, they will be randomized and stratified by the highest weekly mean TSS of disease activity recorded during the screening period (<28 or \geq 28 strata). The IRT will assign patients 1:1 to receive 6 doses of AK002 or placebo.
- Pre-study medications and dietary restrictions should remain unchanged throughout the screening period and throughout the study. Systemic or topical corticosteroids above 10 mg prednisone daily (or the equivalent thereof) will not be allowed, except as a premedication prior to the first infusion only, to treat an IRR that occurs during infusion, or the use is due to unforeseen circumstances when it is deemed medically necessary to treat an unrelated medical condition.
- Eligible patients will receive the first dose of placebo or AK002 (3 mg/kg) on Day 1 with premedication of 80 mg oral prednisone 12–24 hours prior to the start of the infusion.
- If the study drug is well tolerated (no stopping rules being met), patients will receive additional doses of placebo or AK002 (3 mg/kg) on Days 29, 57, 85, 113, and 141. With the exception of Day 1, steroid premedication will only be allowed with the written approval of the Medical Monitor.
- Patients will remain at the site for at least 1 hour of observation following the end of the infusion.

- A repeat EGD and colonoscopy with biopsy will be performed on Day 169 (± 3) or 28 (± 3) days after last dose of study drug if patient early-terminates from the study (between the Day 29 visit and the Day 169 visit).
- Daily administration of the PRO questionnaire (including additional questions) throughout the study and the follow-up period for all patients.
- Patients will rate their impression of disease severity **CCI** [REDACTED] and disease improvement **CCI** [REDACTED] at specified time points during the study.
- Patients will be prompted to answer additional questions about dysphagia and constipation on a daily basis during screening and throughout the study. These will be completed following the PRO questionnaire.
- Follow-up will occur for 84 (± 3) days after last dose of study drug unless patients decide to enter the long-term, open-label extension (OLE) period of the study. Follow-up visits for patients opting not to enter the OLE period of the study will occur on Day 176 (± 3), Day 197 (± 3), and Day 225 (± 3).
- Patients who receive all 6 doses of study drug have the option to receive AK002 by entering into the OLE period of the study if all eligibility criteria for the OLE period are satisfied. Patients who enter into the OLE period of the study may begin the extension dosing 1 day after completing the Day 176 visit of this protocol. Open-label extension patients will not complete the Day 197 or Day 225 procedures under the double-blind period of the study.
- Eligible patients who choose to participate in the OLE period will begin following the OLE Schedule of Assessments ([Table 8](#) in Appendix 13) after completing the Day 176 double-blind period procedures and will receive the first dose of open-label AK002 approximately 1 week after Day 169 (on Day 177).
- Total study duration is approximately 35–37 weeks. For patients entering into the OLE period of the study, the total study duration will be approximately an additional 28-30 weeks.

5.2 Schedule of Events

The overall schedule of procedures and assessments are described in [Table 2](#).

Table 2 Study AK002-021 Schedule of Assessments: Double-Blind Period

Assessment Description	Screening (21–45 days)		Treatment Period (20 weeks)									Follow-Up Period ³⁰ (12 weeks)			
	Baseline ¹	Prior to Day 1	Dose 1 Day 1 ²	Day 8 (±2 days)	Day 15 (±2 days)	Dose 2 Day 29 (±3 days)	Dose 3 Day 57 (±3 days)	Dose 4 Day 85 (±3 days)	Dose 5 Day 113 (±3 days)	Dose 6 Day 141 (±3 days)	Day 169 (±3 days) or 28 days after last dose if ET	Day 176 (±3 days) or 35 days after last dose if ET ²⁹	Day 197 (±3 days) or 56 days after last dose if ET ²⁹	Day 225 (±3 days) or 84 days after last dose if ET	
Informed consent	X														
Demographics	X		X												
Medical History	X		X												
Prior and Concomitant Medications	X		X	X	X	X	X	X	X	X	X	X	X	X	
Body weight and height ²	X		X			X	X	X	X	X		X	X	X	
Vital Signs ³	X		X		X	X	X	X	X	X		X	X	X	
10 or 12-lead ECG ⁴	X														
Complete Physical Exam ⁵	X														
Symptom-Directed Physical Exam ⁶			X		X	X	X	X	X	X		X	X	X	
Baseline Diet Assessment ⁷	X														
Baseline Diet Compliance ⁸			X		X	X	X	X	X	X		X	X	X	
Previous Treatments and Procedure Review	X														
Stool for Ova and Parasite ⁹	X														
Stool antigen test for H. pylori ³²	X														
ePRO Activation and Training ¹⁰	X														
ePRO Questionnaire (will include Additional Questions) ¹¹	<----- Complete electronically 1 time daily ----->														
CCI [REDACTED]	X		X			X	X	X	X	X		X	X		
CCI [REDACTED]	<----- Complete electronically on Screening Day 19, Study Day 7, Study Day 28, and Study Day 225 or ET ----->														
CCI [REDACTED]	<----- Complete electronically on Study Day 7, Study Day 28 and Study Day 225 or ET ----->														
EGD + colonoscopy with Biopsy ^{12,14}	X											X			

Table 2 Study AK002-021 Schedule of Assessments: Double-Blind Period cont.

Assessment Description	Screening (21–45 days)		Treatment Period (20 weeks)								Follow-Up Period ³⁰ (12 weeks)			
	Baseline ¹	Prior to Day 1	Dose 1 Day 1 ²	Day 8 (±2 days)	Day 15 (±2 days)	Dose 2 Day 29 (±3 days)	Dose 3 Day 57 (±3 days)	Dose 4 Day 85 (±3 days)	Dose 5 Day 113 (±3 days)	Dose 6 Day 141 (±3 days)	Day 169 (±3 days) or 28 days after last dose if ET	Day 176 (±3 days) or 35 days after last dose if ET ²⁹	Day 197 (±3 days) or 56 days after last dose if ET ²⁹	Day 225 (±3 days) or 84 days after last dose if ET
Blood for CBC with differential ²¹	X		X	X	X	X	X	X	X	X	X	X	X	X
Blood for Chemistry ^{15,22} (Screening Chemistry includes hCG and FSH)	X		X	X	X	X	X	X	X	X	X	X	X	X
Blood for Serology and Strongyloides stercoralis ¹⁶	X													
Blood for Total Serum IgE ¹⁷	X												X	
Blood for PK ²³	X			X	X	X	X	X	X	X	X	X	X	X
Blood for ADA ²⁴	X		X			X	X	X			X			X
Urine for Urinalysis ²⁵	X					X								X ²⁵
Dipstick Pregnancy Test ²⁶			X			X	X	X	X	X		X	X	
Eligibility Assessment	X	X	X											
Premedication: Prednisone ¹⁹		X												
Access IRT: Stratification and Randomization ¹⁸			X											
Access IRT: IP Kit Assignment			X			X	X	X	X	X				
Study Drug Administration ²⁰			X			X	X	X	X	X				
Non-serious Adverse Events ²⁷			X	X	X	X	X	X	X	X	X	X	X	X
Serious Adverse Events ²⁸			X	X	X	X	X	X	X	X	X	X	X	X
Begin OLE period of the study at least 1 day after Day 176 Visit (if applicable) ^{29,31}											X		Day 197 and Day 225 visits are not applicable for OLE patients	

Table 2 Notes

ADA: Anti-AK002 antibody

ET: Early Termination

IRT: Interactive Response Technology

CBC: Complete blood count

FSH: Follicle-stimulating hormone

CCI

ECG: Electrocardiogram

hCG: Human Chorionic Gonadotropin

CCI

ePRO: electronic Patient Reported Outcome

IP: Investigational Product

PK: Pharmacokinetics

- 1) Baseline screening visit can occur over several days within the screening period. Day 1 can begin as soon as eligibility criteria are met.
- 2) At screening, height (in cm) and weight (in kg) will be recorded. Body weight will also be measured on Days 1, 29, 57, 85, 113, 141, and on follow-up Days 176, 197 and 225 or 28,56, and 84 days after last dose, if ET. Current body weight or body weight from 1 day prior will be used to calculate the amount of AK002/placebo to be mixed with NaCl for the appropriate dose to be administered on each infusion day.
- 3) Vital signs will be measured at screening, Days 176, 197, and 225 or 28,56 and 84 days after last dose if ET and on all dosing days: within 30 minutes predose, 15 (± 5) minutes after the start of study drug infusion, within 15 minutes following the end of infusion and just prior to discharge. Additional vital signs measurements may be collected at the Investigator's discretion if an IRR occurs. Vital signs including systolic and diastolic blood pressure, pulse, body temperature, and respiratory rate will be measured after the patient has been at rest for ≥ 5 minutes and before any blood draws have been obtained (unless collected for an IRR).
- 4) A 10-lead or 12-lead ECG will be obtained at screening before any blood is drawn and after the patient has been in the appropriate position for ≥ 5 minutes.
- 5) A complete physical examination will be performed by either the Investigator or designee and include the following body system or organ assessments: skin; head, eyes, ears, nose and throat; thyroid; lungs; cardiovascular; abdomen; extremities; lymph nodes; and a brief neurological examination.
- 6) A symptom-directed physical exam (including assessment of possible infusion site reactions) will be performed by the Investigator or designee, as needed, if any symptoms are reported.
- 7) A baseline diet assessment ([Appendix 3](#)) will be performed using standardized questions. Eating patterns, food avoidance behaviors, and confirmed allergies will be captured.
- 8) A baseline diet compliance check will be performed at every study visit, except as noted above, and any variances from the baseline diet documented. Patients should maintain the baseline diet throughout the study.
- 9) Fecal collection kits for ova and parasite test will be provided to patients at screening. Collection kits should be returned to the clinical site within 1 day of collection. Negative results must be available prior to randomization.
- 10) Activate PRO questionnaire and provide patient with unique username and password. PRO questionnaire should be activated for all patients on screening Day 1.
- 11) PRO should be completed around the same time each day. Prior to enrollment, the PRO weekly averages of abdominal pain, nausea, and diarrhea over the screening period will be calculated and used to assess eligibility. Weekly average Total Symptom Score (TSS6) will be calculated for eligibility and stratification. Patients will also complete an additional question each about dysphagia and constipation daily during the screening period and throughout the study. The additional questions will be completed following the PRO questionnaire.

Table 2 Notes cont.

12) EGD + colonoscopy with biopsy (performed on the same day whenever possible) will include specimens from the gastric mucosa, duodenum, colon and esophagus (as applicable). Specimens will be processed by the central laboratory. See the Histology Manual for collection, processing, and shipping details. The specimens will be evaluated by a central pathology reader. Additional biopsies will be collected for exploratory analysis. Prior EGD and colonoscopy biopsy samples may be used for eligibility as long as they were performed within 45 days of the AK002-021 screening window for the AK002-021 study and were performed and centrally assessed using the same criteria as for the AK002-021 study, and there were no changes to EoD therapy following the EGD.

13) The **CCI** [REDACTED] is to be completed electronically by patient, in clinic, prior to any blood draw, physical exam, or vital sign measurements.

14) See [Appendix 5](#) for biopsy assessments. The post-treatment EGD + colonoscopy and biopsy assessments will be performed on Day 169 (± 3) or 28 (± 3) days after last dose of study drug if ET. Post-treatment EGD + colonoscopy biopsy results will be blinded to the site.

15) Blood for baseline chemistry, including hCG and FSH, will be collected during the screening period. Only patients of childbearing potential and post-menopausal women are required to have hCG and FSH testing completed.

16) Blood for serology testing will be collected during screening and will include HBsAg, hepatitis C antibody, anti-HBc, and HIV, as well as Strongyloides stercoralis.

17) Blood samples for total serum IgE will be collected during screening and on Day 176 or 35 (± 3) days after last dose of study drug, if ET.

18) Stratification based on TSS of <28 or ≥ 28 will occur. Randomization and stratification will be conducted through the IRT system.

19) Premedication with 80 mg oral prednisone or approved alternative is required 12–24 hours prior to the first infusion. Premedication prior to the start of the second through sixth infusions will only be administered with the prior written approval of the Medical Monitor.

20) Study drug will be administered as a single peripheral intravenous infusion over at least 4 hours for Dose 1 and at least 1 hour for subsequent doses. Refer to the Pharmacy Manual.

21) Blood for CBC with differential, including absolute blood eosinophil count, will be obtained once during screening, Day 8, Day 15, and once during each follow-up visit or ET visit, as well as twice during dosing days just prior to each infusion and 1 hour (± 15 minutes) after the end of each infusion. All differential blood counts from Day 1 (postdose) through the end of the patient's participation will be blinded to the Sponsor and the site. An unscheduled CBC may be collected at the request of the Safety Monitor.

22) Blood for chemistry will be obtained once during screening and once during each follow-up visit or ET visit as well as predose on dosing days.

23) Blood for PK will be obtained predose on dosing Days 29, 57, 85, 113, and 141, as well as during screening and on Days 8, 15, 169, 176, 197, and 225 or 28, 35, 56, and 84 (± 3) days after last dose of study drug if ET.

24) Blood for ADA will be collected at screening and predose on dosing Days 1, 29, 57, and 85, as well as on Days 169 and 225 or 28 and 84 (± 3) days after last dose of study drug if ET. The ADA sample will also be collected any time an immunogenicity-related AE occurs.

25) Urine for standard urinalysis will be obtained at screening, predose on dosing Day 29, ET, and symptom based, as necessary.

Table 2 Notes cont.

- 26) Urine will be collected for dipstick pregnancy test on all infusion days and on Day 176 and Day 197 or 35 and 56 (± 3) days after last dose of study drug, for all patients of childbearing potential. Test kits will be supplied by the central laboratory. Tests will be completed on site and evaluated prior to each infusion.
- 27) The capture of non-serious AE and AESI will begin after the first dose of study drug has occurred.
- 28) The reporting of SAE occurring after signing the informed consent and prior to the first infusion will be limited to those that relate to screening procedures. The capture of all SAE and AE that are not related to screening procedures will begin at the time of first infusion of study drug. For patients participating in the OLE period, AE will be assessed and recorded in the CRF of the AK002-021 double-blind treatment period database up until the start of the first open-label infusion, after the Day 176 visit. The AE will be recorded in the CRF of the AK002-021 OLE period database beginning with the start of the first open-label infusion after Day 176.
- 29) Patients who continue in the OLE period of the study will complete the procedures for Day 176 and may begin open-label dosing in the OLE period of the study, if eligible, 1 day after completion of the Day 176 visit. In this case, patients will not complete the Day 197 or Day 225 procedures under the double-blind period of the study.
- 30) The ET visits should be conducted 28, 35, 56, and 84 (± 3) days after last dose of study drug or prior to this, if necessary, to ensure compliance with the visit. If only 1 ET visit is possible, EGD + colonoscopy and end-of-study procedures may occur on the same day. If the end-of-study visit occurs more than 35 days after last dose of study drug, then perform the visit as soon as possible. The procedures listed under the 28-day and 35-day post-study drug visit will be conducted unless otherwise directed by the Medical Monitor. For patients participating in the OLE period, AE and concomitant medications should be collected and recorded in the AK002-021 double-blind treatment period database up until the start of the first open-label infusion after the Day 176 visit. This includes prednisone premedication administered after the Day 176 visit of the OLE period, which should be recorded in the Concomitant Medications CRF of both the AK002-021 double-blind treatment period database and the AK002-021 OLE period database.
- 31) The final hematology assessment for the double-blind period of the study **must** be collected **prior to** the patient taking prednisone premedication for the first dose of the OLE period. Therefore, dosing in OLE must take place at least 1 day after completion of the Day 176.
- 32) Stool antigen test for *H. pylori* will be obtained to confirm that no existing active *H. pylori* infection is present. Fecal collection kits (same container as for ova and parasite testing) should be returned to the clinical site within 1 day of collection. Negative results must be available prior to randomization. If *H. pylori* is detected in tissue biopsies by the central pathologist, the patient should be excluded from the study. In case of a positive test, the patient must be screen-failed. After *H. pylori* treatment and an additional 6 weeks later, patient may be reconsented and will receive a new patient number.

6. Criteria for Evaluation

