12.1 Screening Period

- 1) Obtain written informed consent.
- 2) Assign the participant a PID.
- 3) Begin the collection of SAE related to any screening activities.
- 4) Collect demographics and medical history.
- 5) Record prior and concomitant medications.
- 6) Determine body weight and height.
- 7) Activate patient access to the ePRO questionnaire portal and instruct patient on use of the website to complete the questionnaire(s). Use the ePRO Teaching Tool to instruct the patient on use of the electronic platform (Appendix 7).
- 8) **CCI** [REDACTED] to be completed by the patient.
- 9) Perform baseline diet assessment.
- 10) Complete previous treatments and procedure review.
- 11) Obtain vital signs before blood draws and after patient at rest ≥ 5 minutes.

- 12) Perform a complete physical examination.
- 13) Obtain a 10-lead or 12-lead ECG before blood draw.
- 14) Collect the following samples for the central laboratory:
 - a) Blood for CBC with differential
 - b) Blood for Chemistry (sample to be tested for FSH and hCG if patient is of childbearing potential)
 - c) Urinalysis
 - d) Blood for serology testing (includes *Strongyloides stercoralis*)
 - e) Blood for PK
 - f) Blood for ADA
 - g) Blood for total serum IgE
- 15) Provide patient a stool collection kit and ask patient to provide a stool sample while on site or return it to the site within 1 day of collection.
- 16) Perform a screening EGD and colonoscopy with biopsy following instructions provided by Allakos any time during the screening period. The EGD and colonoscopy should take place on the same day in order to minimize effects of procedure premedication on the PRO scores. Patient should arrive fasting for the EGD procedure as specified by instructions from the EGD provider.
- 17) **CC1** to be completed by the patient on screening Day 19 (not a clinic visit).
- 18) Using results from the central histology reader, confirm that the eosinophil count from the gastric and/or duodenal biopsies qualify the patient for the study and no exclusionary criteria are found on the EGD or colonoscopy.
- 19) Review all ePRO scores. Since the bowel preparations could artificially increase the scores, exclude ePRO scores from the day before and the day of colonoscopy when assessing eligibility criteria.

12.2 Prior to Day 1

The following procedures will be performed prior to Day 1:

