- 12) Blood for ADA will be obtained predose on OLE Dose 1 and on Day 372 or ET. For OLE Doses 2, 3, 4, 5 and 6, blood for ADA will be obtained only if a suspected immunogenicity-related AE occurs.
- 13) Urine for urinalysis will be obtained predose on OLE Dose 1, OLE Dose 2, and Day 372.
- 14) For females of childbearing potential, urine will be collected, tested, and pregnancy result confirmed predose on all dosing days.
- 15) All patients will self-administer 80 mg oral prednisone 12–24 hours prior to the first infusion. An approved alternative(s) may be used with the approval of the Medical Monitor. Premedication may be administered prior to subsequent infusions at the Investigator's discretion, but only with written approval from the Medical Monitor. This dose of prednisone premedication prior to the first infusion must be administered *after* all double-blind Day 176 assessments are performed and should be recorded in the Concomitant Medications CRF of both the AK002-021 double-blind treatment period database and the AK002-021 OLE period database.

Table 8 Notes cont.

- 16) Open-label AK002 will be administered as a single peripheral intravenous infusion over at least 4 hours on OLE Dose 1 and over at least 1 hour on subsequent dosing days. Refer to the AK002-021 Pharmacy Manual for detailed administration and infusion rate schedule instructions.
- 17) Patients will remain under observation at the site for at least 1 hour after the end of each infusion. In the event of an IRR, the patient may require prolonged observation (>1 hour or until the symptoms resolve), as per the Investigator's discretion. Patients will also be instructed to immediately contact the study doctor if any reactions occur after discharge.
- 18) If a new or worsening symptom (or clinically significant finding) is observed or reported, the Investigator or designee will determine whether a symptom-directed physical examination is warranted and should perform it at any time or multiple times during a visit (predose, during infusion, and/or postdose).

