**Table 2 Terminology and Definitions cont.**

Terminology	Definition
Patient-Reported Outcome cont.	
 
• Diarrhea intensity
 
• Diarrhea frequency
 
• Fullness before finishing a meal (Early satiety) intensity
 
• Loss of appetite intensity
 
• Bloating intensity
 
• Abdominal cramping intensity
 

	Each intensity evaluation is scored on a scale of 0=none to 10=worst possible.
Prior Medication	Medication collected on the Prior/Concomitant Medication CRF, with start date prior to Study Day 1.
PRO Total Symptom Score	Total symptom score (TSS) is the sum of 6 (abdominal pain, abdominal cramping, bloating, nausea, early satiety, and loss of appetite) weekly average symptom intensity scores.
Study Day	Study Day 1 is defined as the date on which a subject took the first dose of study drug. Other study days are defined relative to Study Day 1. For visits prior to the first dose of study drug, Study Day is calculated as Visit Date – Day 1 Date. For visits after the first dose, Study Day is calculated as Visit Date – Day 1 Date +1.
Study Drug	AK002 or placebo administered by IV infusion.
Study Week	Study Week for PRO analysis is defined as 7 days a week starting from the day of first dose (Day 1).
Tissue Eosinophil Responder in EoD	Mean duodenal eosinophil count $\leq$ 15 cells/hpf in 3 highest duodenal hpf.
Treatment-emergent	Adverse events reported in the clinical database with a date of onset on or after the start date of the first dose of the study drug.
Treatment Responder	Subject with >30% improvement in TSS from baseline and mean eosinophil count $\leq$ 15 cells/hpf in 3 highest duodenal hpf.

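### Non-serious events in the 12–24 hours between the required prednisone and the first infusion are not captured as adverse events, and the reporting duty for serious ones is unclear

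*Protocol*

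**What the plan says.** **Premedication.** Protocol Table 2 note 19: "Premedication with 80 mg oral prednisone or approved alternative is required 12–24 hours prior to the first infusion". The patient takes it at home (section 12.2).

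**Start of capture.** Note 27: "The capture of non-serious AE and AESI will begin after the first dose of study drug has occurred". Note 28 adds: "The capture of all SAE and AE that are not related to screening procedures will begin at the time of first infusion of study drug". Sections 8, 13.1 and 13.7.1 set the same start for adverse events. The SAP repeats both notes under its own Table 1.

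**Serious events before infusion 1.** Under note 28, the reporting of SAEs after consent and "prior to the first infusion will be limited to those that relate to screening procedures". The first steps of section 12.1 agree: "Begin the collection of SAE related to any screening activities". Section 13.2 has the same limit. Section 13.7.2, by contrast, asks sites to report any SAE seen during the study within 24 hours, whatever its cause.

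**Day 1 before the infusion.** Section 12.3 asks the site to check for SAEs related to screening procedures, and to document changes in health status and concomitant medication.

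**Extension.** Table 8 note 15: "All patients will self-administer 80 mg oral prednisone 12–24 hours prior to the first infusion". For patients who enter the extension, note 28 keeps AEs in the "double-blind treatment period database up until the start of the first open-label infusion, after the Day 176 visit".

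**Treatment-emergent.** SAP Table 2 ties the term to the date study drug is first given: "Adverse events reported in the clinical database with a date of onset on or after the start date of the first dose of the study". Protocol section 15.7 has a similar rule that also covers worsening. Neither definition states an end, but protocol section 7.6 closes collection at the start of open-label drug, at Day 225, or 84 days after the last dose.

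**The concern.** The protocol makes every patient take a sizeable corticosteroid dose and then opens the adverse-event record only at or after the infusion that follows. Early effects of that dose have no place in the AE data. This matters in three ways.

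- The AE tables would describe the tolerability of the scheme as given, without the first hours of one of its components.
- A symptom that began after the prednisone and continued into the infusion has no earlier AE entry. Headache, nausea and flushing are among the listed symptoms of infusion-related reactions, which are events of special interest. Such a symptom is then harder to tell apart from a reaction to the infusion.
- A site facing a serious event in this window finds two rules that disagree.

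The same prednisone is required again before the first open-label infusion. There the window falls inside AE recording, so the two uses of one drug are treated differently.

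**Working it through.** No power or sample-size figure is involved. The check puts the rules on one timeline.

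**1. Length of the first window.** Prednisone is taken 12–24 h before the start of infusion 1. Capture opens at the infusion (note 28) or after the first dose (note 27). Under note 28 the gap is 12–24 h. If note 27 means after the end of an infusion lasting at least 4 h (note 20), the gap is at least 12 + 4 = 16 h to 24 + 4 = 28 h. The two notes should say the same thing.

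**2. Size.** With about 80 patients: 80 × 12 h = 960 h = 40 patient-days, and 80 × 24 h = 1,920 h = 80 patient-days. No event rate is given, so an expected number of events cannot be derived.

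**3. What happens to an event in that window.**

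| Event before infusion 1 | Rule | Result |
|---|---|---|
| Non-serious | Notes 27–28; sections 8, 13.1, 13.7.1 | Not an AE; noted at most as a change in health status (12.3) |
| Serious, related to a screening procedure | Note 28; 12.1, 13.2, 13.7.1 | Reported from consent |
| Serious, after prednisone | Note 28 and 13.2 against 13.7.2 | Unclear |

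The third row turns on whether the prednisone is a screening procedure. Table 2 puts it in the screening block, under the column before Day 1. The visit text puts it in section 12.2, apart from the screening period in 12.1. Neither settles the question.

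**4. Patients never infused.** Eligibility is confirmed again on Day 1, after the prednisone (12.3). A patient who took it and then fails that check is outside the Safety population, which requires at least one infusion (protocol 15.2, SAP 6.1.1).

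**5. Comparison between arms.** All patients take the same prednisone (section 7.1). Table 2 and section 12.3 place randomization on Day 1, after the prednisone; section 10.2 also allows the day before. Either way, no study drug has been given in the window.

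**6. Extension window.** The extension prednisone follows the Day 176 assessments and precedes the first open-label infusion by 12–24 h. Events in between go to the double-blind database and meet the treatment-emergent definition.
- Phase 2 extension uptake was above 90% (section 2.3). If 90% applied here, 0.90 × 80 = 72 patients would have this window. That is an assumption: entry here requires all 6 infusions and the Day 176 visit, and each 10 points of uptake is 8 patients.
- As a share of about 176 days of follow-up: 0.5/176 = 0.3% to 1/176 = 0.6%.
- The last randomized dose is on Day 141, so 176 − 141 = 35 days earlier. Exclusion criterion 19 equates 5 half-lives with 4 months. Taking that as 120 days, one half-life is 24 days, and 35/24 is about 1.5 half-lives. AK002 is still present when the extension prednisone is taken.

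**The case against.** The best defence is that AE capture is tied to study drug, which the protocol defines as AK002 or placebo. That is an ordinary design choice, and the prednisone is background given alike to both arms. This stands as far as the treatment comparison goes. It does not explain why effects of a drug the protocol itself requires should stay out of the AE record.

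Four stronger readings are tempting and are not supported.

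- **That these events go wholly unrecorded.** Section 12.3 has the site document changes in health status before the infusion, with vital signs, blood tests and an examination if needed. The accurate statement is that they are not entered as adverse events.
- **That serious events are excluded.** The rules conflict; they do not clearly exclude. Section 13.7.2 can be read to require the report, and the prednisone might count as a screening procedure.
- **That the comparison of AK002 with placebo is biased.** Both arms take the prednisone before any study drug, so the gap does not by itself favour either arm.
- **That events after the extension prednisone are wrongly booked to the randomized arm.** Until the open-label infusion the only study drug received is the randomized one, given about five weeks before and not yet cleared. Keeping these events is a consistent rule, and section 7.6 bounds it. Ending the treatment-emergent period at the prednisone could drop late AK002 events.

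One asymmetry remains. Table 2 note 31 requires the last double-blind hematology sample to be taken before the extension prednisone, while AE data have no marker for that intake. This supports a flag, not a cut-off.

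**Conclusion.** The concern holds as a gap in safety capture at the start of treatment. By stated rule, non-serious events in the 12–24 hours after the required prednisone are not adverse events in this trial, and the duty to report a serious one is unclear. The gap covers about 80 patients and 40–80 patient-days, assuming all take the premedication in the stated interval; patients who take it and are not infused come on top. No efficacy analysis is touched. The number of events missed cannot be estimated from the documents. The change is worth making because it is cheap and the information cannot be fully rebuilt later. The extension rule can stay, with a flag.

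**What to change.** 1. In Table 2 notes 27–28, sections 8, 13.1, 13.2 and 13.7.1, the Day 1 pre-infusion step in 12.3, and the notes copied into SAP Table 1, start AE and SAE capture at the first prednisone premedication intake. Use one wording for the start in both notes.
2. Reconcile notes 27–28 and section 13.2 with section 13.7.2, so that a serious event after the prednisone and before infusion 1 has one answer.
3. In the SAP, list events with onset from that intake to infusion 1 as premedication-period events, outside the treatment-emergent tables. Base the listing on everyone who took the premedication, infused or not. The current treatment-emergent rule works on dates, so an onset early on Day 1 would count as treatment-emergent once entered; use onset time or a before/after-infusion field. State whether later worsening counts, since protocol 15.7 includes it and the SAP does not.
4. For the extension, keep events up to the first open-label infusion in the double-blind tables, and flag in the listing those with onset after the extension prednisone. That intake is already recorded in both databases.

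The cost is protocol, CRF-guideline and SAP wording, one timing field, and a few more AE entries before Day 1 dosing. No treatment or visit changes.
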